Mindfulness-based interventions, such as mindfulness-based cognitive therapy (MBCT), have the potential in improving psychological health in older people. MBCT is a group intervention originally designed to prevent recurrent depressive disorders (Segal et al., 2012). It combines mindfulness practices and cognitive-behavioural elements to enhance an individual's understanding of the interacting relationships among thoughts, emotions, bodily sensations, and behaviours. Mindfulness practice emphasizes on developing a moment-to-moment, non-judgmental awareness and may be helpful in alleviating depression by directing individual's attention to the present instead of ruminating in the past. Systematic reviews have shown the efficacy of MBCT in reducing depression, anxiety, loneliness, stress, sleep problems, ruminations, general mood, and positive affect (Geiger et al., 2016; Thomas et al., 2020). However, over half of the included studies lacked a control group and mixed findings were observed possibly because of inconsistent modifications to the protocol, methodological flaws, and study limitations.

The application of MBCT in the Chinese older population is understudied. Recently, a randomized controlled trial on MBCT for older people were conducted in Hong Kong. Shih et al. (2021) compared a standard MBCT to an active control group (physical exercise + health education) for older people with depression and revealed that, while both groups showed a reduction in the severity of depressive symptoms, only the MBCT group showed improvement in mindfulness.

With these promising findings, more studies are needed to establish the evidence base for the intervention and inform clinical practice in this population. We aim to explore whether a modified MBCT based on older people's feedback can reduce depressive symptoms and

improve mindfulness. With the growing older people population, there is a need for greater social welfare capacity to promote their well-being, we also examine whether a modified MBCT led by social workers under the supervision of a mindfulness teacher can benefit the population.

Objectives

- To evaluate the effectiveness of MBCT in improving mental health and mindfulness in older people with depressive symptoms as compared to care as usual
- To compare the effectiveness between MBCT led by mindfulness teacher and that led by social workers
- To examine psychological flexibility as a potential mechanism of change

Methods

Design

This is a non-randomised controlled trial with three arms, comparing older people with mild to moderately severe depressive symptoms receiving modified MBCT led by a mindfulness teacher, MBCT led by social workers, and care as usual.

Participants

Participants will be recruited from District Elderly Community Centres (DECC) and Integrated Community Centre for Mental Wellness (ICCMW). We aimed to recruit 32 participants for each arm, totaling 96 participants in the study. They will be included if they are aged (1) 60 years or older, (2) have depressive symptoms of mild level or above, as indicated by scoring 5 or more in PHQ-9, and (3) can give informed consent to participate. The exclusion criteria are (1) known history of autism, intellectual disability, schizophrenia-spectrum disorder, bipolar disorder, Parkinson's disease, or dementia, (2) imminent suicidal risk, and (3) difficulty in communication.

Intervention

The MBCT protocol has been modified according to our pilot test with older people with depressive symptoms and suggestions from existing literature in teaching mindfulness to the older population. It consists of eight 2-hour weekly sessions, but the whole day retreat is excluded. Each session contains guided mindfulness exercises, feedback and discussion,

homework review, and psychoeducation. The programme is conducted in Cantonese and led by either a MBCT teacher who received formal training organized by the Oxford Mindfulness Centre and the Hong Kong Centre for Mindfulness or a social worker supervised by the MBCT teacher. The care as usual group received usual service provided in DECC and ICCMW.

Outcomes

Demographic information will be collected at baseline. All outcome measures will be collected at baseline (T0), 8-week (T1: immediately after the intervention), and 12-week (T2). The questionnaires are self-administered but trained social workers or research assistants will provide support in completing the questionnaire when needed. The questionnaire is expected to last for roughly 30 minutes.

Depressive symptoms will be assessed using the validated Chinese version of the Patient Health Questionnaire (PHQ-9; Wang et al., 2014). The 9-item instrument incorporates depression diagnostic criteria with other leading major depressive symptoms and rates the frequency of the symptoms on a four-point Likert scale ranging from 0 (*not at all*) to 3 (*nearly every day*). PHQ-9 scores of 5-9, 10-14, 15-19, 20 and above represent mild, moderate, moderately severe, and severe depression.

Anxiety symptoms will be assessed adopting the validated Chinese version of the Generalized Anxiety Disorder 7-item scale (GAD-7; Tong et al., 2016). The instrument taps on the most prominent diagnostic features for GAD and rates the frequency of symptoms on a four-point Likert scale, ranging from 0 (*not at all*) to 3 (*nearly every day*). GAD scores of 5, 10, and 15 are taken as the cut off points for mild, moderate, and severe anxiety, respectively.

Stress will be measured by the Chinese validated Perceived Stress Scale (PSS; Ng, 2013). The 10-item instrument measures the degree to which an individual's life situations are perceived as stressful. Respondents rate the frequency of how they felt a certain way during the last month on a Likert scale ranging from 0 (*never*) to 4 (*very often*). Higher scores indicate higher perceived stress.

Mindfulness will be assessed using the Chinese validated Five Facet Mindfulness Questionnaire Short Form (FFMQ-SF; Hou et al., 2014). The 20-item instrument measures

mindfulness by five domains: ‘observe’, ‘describe’, ‘acting with awareness’, ‘non-judging’ and ‘non-reactivity’. Respondents rate how much each statement reflects their lives on a 5-point Likert scale ranging from 1 (*never*) to 5 (*always*). Higher scores indicate higher mindfulness.

Psychological flexibility will be assessed using the 8-item abbreviated version of the Comprehensive assessment of Acceptance and Commitment Therapy processes (CompACT-8; Morris, 2019), which has been translated into Chinese for use in the current study. The instrument measures psychological flexibility by three domains: ‘openness to experience’, ‘valued action’, and ‘behavioural awareness’. Respondents rate the items on a 7-point Likert scale, ranging from 0 (*strongly disagree*) to 6 (*strongly agree*). Higher scores indicate greater psychological flexibility.

Data analysis

Baseline demographic information and outcome measures among the three groups will be compared using independent sample t-test. Mixed ANOVA will be used to compare outcome changes from T0 to T2 among the groups. Post-hoc analyses, such as pairwise comparisons, will be performed to identify groups with significant changes. All results will be reported with appropriate effect sizes, statistical significances, and confidence intervals. If the findings demonstrate intervention effects, a regression model will be conducted to examine whether psychological flexibility (change scores) are associated with lower depressive symptoms post intervention, while controlling for baseline depression.

References

- Geiger, P. J., Boggero, I. A., Brake, C. A., Caldera, C. A., Combs, H. L., Peters, J. R., & Baer, R. A. (2016). Mindfulness-Based Interventions for Older Adults: a Review of the Effects on Physical and Emotional Well-Being. *Mindfulness*, *7*(2), 296–307. <https://doi.org/10.1007/s12671-015-0444-1>
- Morris, J. (2019). *Development and validation of a short form of the Comprehensive assessment of Acceptance and Commitment Therapy processes (CompACT-SF)*. University of Nottingham.
- Ng, S. (2013). Validation of the 10-item Chinese perceived stress scale in elderly service workers: one-factor versus two-factor structure. *BMC Psychology*, *1*(1), 9. <https://doi.org/10.1186/2050-7283-1-9>
- Segal, Z. V., Williams, J. M. G., & Teasdale, J. D. (2012). *Mindfulness-based cognitive therapy for depression*. Guilford Press.
- Shih, V. W., Chan, W.-C., Tai, O.-K., Wong, H.-L., Cheng, C. P., & Wong, C. S. (2021). Mindfulness-Based Cognitive Therapy for Late-Life Depression: a Randomised Controlled Trial. *East Asian Archives of Psychiatry*, *31*(2), 27–35. <https://doi.org/10.12809/eaap2075>
- Sun, W. J., Xu, L., Chan, W. M., Lam, T. H., & Schooling, C. M. (2012). Depressive symptoms and suicide in 56,000 older Chinese: a Hong Kong cohort study. *Social Psychiatry and Psychiatric Epidemiology*, *47*(4), 505–514. <https://doi.org/10.1007/s00127-011-0362-z>

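### Eligibility does not require availability for, or willingness to attend, the MBCT sessions, so people who cannot or will not attend may enter care as usual disproportionately

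*Combined protocol and SAP*

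**What the plan says.** All references are to the combined protocol and SAP.

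- **Methods, Design.** "This is a non-randomised controlled trial with three arms". The arms are described by what participants receive. No rule is given for how or when a person comes to be in one arm or another.
- **Methods, Participants.** There are three inclusion criteria. The first is age 60 or over; the other two read "2) have depressive symptoms of mild level or above, as indicated by scoring 5 or more in PHQ-9, and (3) can give informed consent to" take part. There are three exclusions: a list of diagnoses, then "imminent suicidal risk, and (3) difficulty in communication". Recruitment is through two kinds of community centre. On size: "We aimed to recruit 32 participants for each arm, totaling 96 participants in the study".
- **Methods, Intervention.** Of the modified MBCT programme: "It consists of eight 2-hour weekly sessions, but the whole day retreat is excluded". Also: "The programme is conducted in Cantonese and led by either a MBCT teacher" or a supervised social worker. The comparison arm gets the centres' ordinary services.
- **Methods, Outcomes.** Demographic information is collected at baseline, but the items are not listed.
- **Data analysis.** The arms are compared by mixed ANOVA with no covariates named. Baseline depression is controlled only in the later regression on psychological flexibility, which is run only if an intervention effect is found.

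**The concern.** MBCT asks something of participants that care as usual does not. A person who scores 8 on the PHQ-9 but cannot come for two hours each week, or does not want a mindfulness class, meets every written criterion. In a randomised trial such people would be spread over the arms by chance. Here nothing does that. If they tend to end up in care as usual, entry to the MBCT arms carries an unwritten condition (available and willing) that the comparator lacks.

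The first objective rests on comparing MBCT with care as usual. Both MBCT arms are set against the same comparator, so both contrasts are exposed, on every outcome. A difference produced by who entered each arm would look like a treatment effect. It could also trigger the mechanism regression, which depends on an effect having been shown.

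**Working it through.** **Step 1. Does any criterion cover attendance?**

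| Criterion | Availability | Willingness to attend MBCT | Following a Cantonese group |
|---|---|---|---|
| Age 60 or over | no | no | no |
| PHQ-9 of 5 or more | no | no | no |
| Can consent | no | no (consent is to the study, which includes care as usual) | no |
| Listed diagnoses | no | no | no |
| Imminent suicidal risk | no | no | no |
| Difficulty in communication | no | no | partly (term undefined) |

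Availability and willingness are covered by nothing. Language is covered in part.

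**Step 2. What does each arm demand?** MBCT: 8 sessions x 2 hours = 16 hours of group attendance. Care as usual: no sessions. The written entry conditions are the same for all arms, but the demands are not.

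**Step 3. Does the analysis deal with it?** The group comparison names no covariates. Baseline scores and demographics are collected and could serve as partial proxies, but the plan does not use them in this comparison. Willingness is not listed among the data.

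**Step 4. The plan's own figure.** 3 arms x 32 = 96, which agrees with the stated total. No alpha, power, effect size, SD or dropout rate is given. The point does not depend on the sample size, which is used below only for scale.

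**Step 5. How large could the bias be?** The documents give no inputs, so these are assumptions:

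- f = share of the care-as-usual arm who could not or would not attend, with none in the MBCT arm
- g = difference in their mean outcome change from that of willing attenders, in SD units
- a simple comparison of two means, 32 per arm, two-sided alpha 0.05, normal approximation, no true effect

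Bias b = f x g. Standard error = sqrt(2/32) = 0.25 SD. Rejection rate = Φ(b/0.25 − 1.96) + Φ(−b/0.25 − 1.96).

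| f | g | b (SD) | b/0.25 | Rejection rate |
|---|---|---|---|---|
| 0.10 | 0.2 | 0.02 | 0.08 | 5.1% |
| 0.25 | 0.5 | 0.125 | 0.50 | 7.9% |
| 0.50 | 0.8 | 0.40 | 1.60 | 36% |

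For scale, 32 per arm gives 80% power for 0.25 x (1.96 + 0.84) = 0.70 SD.

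In PHQ-9 points, again on assumed inputs: f = 0.2 and a 1-point difference give 0.2 x 1 = 0.2; f = 0.5 and a 2-point difference give 0.5 x 2 = 1.0.

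**Step 6. Direction.** The sign of b is the sign of g. If non-attenders do worse than willing attenders, the bias favours MBCT; if they do better, it works against MBCT. The rejection rates above are the same either way. The documents say nothing about the prognosis of non-attenders.

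**The case against.** The strongest objection is that no allocation rule is stated. A reader might infer that people unable or unwilling to attend can only be placed in care as usual. The documents do not support that. If arms were set by centre or recruitment period, and the arm was unknown at enrolment, such people could enter an MBCT arm and simply not attend. Entry would then not differ between arms, and the result would be dilution of any effect. This stands, and it is why the point says disproportionately and not exclusively. It does not dispose of the concern: if people know their arm when they consent, those consenting to MBCT know that they must attend, and the others face no such condition. Nothing in the plan rules this out.

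Four further objections have force.

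- **Direction.** It is tempting to say that the bias favours MBCT. Frailty might go with a worse course, but paid work, caregiving or dislike of the class need not. The direction is open.
- **Language and reach.** The communication exclusion may screen out some people who cannot follow Cantonese, and recruitment through community centres probably limits the number who are housebound. Neither touches willingness or competing commitments.
- **Later adjustment.** A reader might conclude that it could not help at all. Because the demographic items are not listed, some may bear on availability, and baseline severity is a partial proxy. The supportable statement is that adjustment cannot fully repair the problem.
- **Root cause.** The unstated allocation method is the larger gap. A willingness threshold does not equalise motivation, so it reduces selection without removing it. That limits what the fix achieves but is no reason to leave the criterion out.

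**Conclusion.** The concern holds in this form. The eligibility criteria contain no requirement to be available for and willing to attend the sessions. With non-random arms, no stated allocation rule and a comparator that needs no attendance, people who cannot or will not take MBCT are eligible and may enter care as usual disproportionately. That would confound both MBCT versus care-as-usual contrasts, and the planned unadjusted mixed ANOVA does not deal with it.

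The absence of the criterion is a matter of record. That non-attenders would concentrate in care as usual is an inference, plausible where the arm is chosen or known at enrolment. Size and direction cannot be determined from the documents. The 0.02 to 0.40 SD range, and the 0.2 to 1.0 PHQ-9 points, show only that assumed inputs can make the bias negligible or serious.

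**What to change.** 1. Add a fourth inclusion criterion, identical for all three arms: *is available for and willing to attend eight weekly 2-hour group sessions conducted in Cantonese*.
2. Have it confirmed and recorded before the person's arm is known. For this to be workable, the plan must also say how and when the arm is determined.
3. State that a person who declines or cannot attend MBCT is a screen failure and may not be entered as care as usual.
4. In reporting the first objective, acknowledge that confounding from non-random allocation remains, since the criterion reduces it without removing it.

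The cost is one criterion and one screening question, a somewhat smaller pool for care as usual, and results that apply to people willing to take a group programme. The change belongs before enrolment, because the plan does not provide for recording willingness and it could not be reliably reconstructed later.

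### Centre type and recruitment period are neither balanced across the three non-randomised arms nor in the outcome model, so the MBCT versus usual-care contrast can be confounded by centre type

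*Combined protocol and SAP*

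**What the plan says.** All references are to the combined protocol and SAP.

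- Methods, Design: "This is a non-randomised controlled trial with three arms". No rule is given for how people or centres come to be in an arm.
- Methods, Participants: recruitment is from District Elderly Community Centres (DECC) and Integrated Community Centres for Mental Wellness (ICCMW). This is stated for the study as a whole, not by arm. The only target is "We aimed to recruit 32 participants for each arm, totaling 96 participants in the study".
- Methods, Intervention: "The care as usual group received usual service provided in DECC and ICCMW". The content of that service is not described, and the text does not say whether MBCT participants keep access to it.
- Objectives, first item: "To evaluate the effectiveness of MBCT in improving mental health and mindfulness in older people with depressive symptoms as compared to care as usual".
- Data analysis: "Baseline demographic information and outcome measures among the three groups will be compared using independent sample t-test", and then "Mixed ANOVA will be used to compare outcome changes from T0 to T2 among the groups". No term for centre, centre type or period is named. Baseline depression is controlled only in the later regression on psychological flexibility.

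**The concern.** Without randomisation, the first objective needs the arms to be alike in whatever else drives change over the 12 weeks. Centre type is an obvious candidate. One type serves older people generally and the other is, by its name, a mental wellness service, so the background support and the kind of person who attends may differ. The plan would allow the MBCT places to be filled mostly at one type and the usual-care places mostly at the other, or the arms to be recruited at different times.

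MBCT is delivered in groups, so an arm of 32 is made up of a few classes. If classes draw on the centre that hosts them (an assumption), the mix can shift in large steps without any departure from protocol.

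The planned analysis does not guard against this. Looking at change from T0 deals with stable differences in level, but not with different support received after T0. The baseline comparison may reveal an imbalance in what was measured, but no consequence for the outcome model is stated. The bias could run either way, creating an apparent benefit or hiding a real one.

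**Working it through.** **The plan's own figure.** 3 × 32 = 96, which agrees. The 32 per arm cannot be derived, because no alpha, power, effect size, SD or dropout is given.

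**Inputs.** From the plan: 32 per arm, so 32 v 32 for one MBCT arm against usual care, or 64 v 32 with the MBCT arms pooled. Assumed: two-sided alpha 0.05; no true MBCT effect; *g*, the difference in outcome change between centre types, 0.2 or 0.3 SD; *m*, the difference between arms in the share of participants from one centre type, 0.50.

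**Bias.** Bias = *g* × *m*.
- 0.2 × 0.50 = 0.10 SD
- 0.3 × 0.50 = 0.15 SD

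If the PHQ-9 SD is 4–5 (assumed), this is 0.10 × 4 = 0.4 points at the low end and 0.15 × 5 = 0.75 points at the high end.

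**False-positive rate.** SE = √(1/n₁ + 1/n₂) in SD units, and the rejection rate is Φ(bias/SE − 1.96) + Φ(−bias/SE − 1.96).

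For 32 v 32, SE = √(1/32 + 1/32) = 0.25. With bias 0.15, bias/SE = 0.60, so the rate is Φ(−1.36) + Φ(−2.56) = 0.087 + 0.005 = 0.092.

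| *g* (SD) | *m* | Bias (SD) | 32 v 32 | 64 v 32 |
|---|---|---|---|---|
| any | 0 | 0 | 5.0% | 5.0% |
| 0.2 | 0.25 | 0.050 | 5.5% | 5.6% |
| 0.2 | 0.50 | 0.100 | 6.9% | 7.5% |
| 0.3 | 0.25 | 0.075 | 6.0% | 6.4% |
| 0.3 | 0.50 | 0.150 | 9.2% | 10.7% |

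**Scale.** Under the same alpha, 32 v 32 has 80% power at about 0.70 SD. A bias of 0.10–0.15 SD is 0.10/0.70 = 14% to 0.15/0.70 = 21% of that.

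**What within-type results could show.** With an even split, each type contributes 16 v 16. The 95% half-width is 2.04 × √(1/16 + 1/16) = 2.04 × 0.354 = 0.72 SD. With the MBCT arms pooled (32 v 16) it is about 0.62 SD. Both are several times the illustrated bias, so within-type contrasts cannot test for it.

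**The case against.** The strongest reply is that the documents show no imbalance. The comparator sentence names both centre types, and read plainly it means that the usual-care arm draws on both. Neither type's usual service is described, so a difference between them is inferred from their names. Both *g* and *m* above are assumptions. Centre type is known at T0, so a partial imbalance could be adjusted for. The wider problem is non-random allocation with no stated rule, of which centre type is only one part.

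Much of this stands, and it rules out four stronger readings that a reader might infer:

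- *That arm and centre type may coincide completely.* This would need the usual-care arm to come from one type only, which sits badly with the sentence that defines it.
- *That the two services are known to differ in effect.* The documents do not say so.
- *That usual service is withheld from MBCT participants.* The text is silent. What can be said is that continued access is not stated.
- *That no baseline adjustment can help.* Adjusting for baseline PHQ-9 alone would not, but adjusting for centre type can, provided that both types are represented in each arm.

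The gap itself remains. Drawing on both types fixes neither the proportion in the usual-care arm nor the mix in the two MBCT arms. No text makes the arms concurrent. An adjustment that could be made is not planned.

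**Conclusion.** The concern holds as a design and analysis gap. The arms may differ in centre type and calendar period, and nothing in the plan prevents this or adjusts for it, so the contrast for the first objective can be confounded by centre type and its background service. It is not shown that this will happen.

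The size cannot be computed from the documents. With an assumed 0.2–0.3 SD difference in change between centre types and an assumed 50-point difference in mix, the bias is 0.10–0.15 SD, and the false-positive rate for 32 v 32 is about 7–9% instead of 5%. That is moderate, but it is worth preventing because the change is cheap. No size is offered for differences in calendar period, since the documents give nothing on which to base one.

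**What to change.** 1. Within the existing 96 places, recruit all three arms to about the same DECC:ICCMW split, over the same calendar period as far as class scheduling allows.
2. Record centre type for every participant.
3. Add centre type as a factor in the outcome model for MBCT versus usual care, with its interaction with time, because the effect of interest is a difference in change.
4. Show the differences within each centre type descriptively only.
5. State whether usual service remains available in all three arms. If it does, define the first objective as MBCT plus usual service versus usual service alone.
6. State self-selection and differences between individual centres as remaining limitations. Balance on centre type does not address them.

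The costs are somewhat slower filling of places, a possible need to hold classes at both centre types, one between-participant degree of freedom, and (2 − 1) × (3 − 1) = 2 more for the interaction with time. No added participants are needed. Parts of the Methods are in the past tense, which leaves open whether recruitment can still be steered. If it cannot, items 2 to 6 still apply, and the centre mix and recruitment dates of each arm should be reported.

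### Non-randomised three-arm trial with no covariates in the between-arm effect analysis, and a baseline check that uses a two-group test and leads to no action

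*Combined protocol and SAP*

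**What the plan says.** The Design section states: "This is a non-randomised controlled trial with three arms". No allocation rule, matching or other balancing is described.

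Two of the three objectives compare arms: "To evaluate the effectiveness of MBCT in improving mental health and mindfulness in older people with depressive symptoms as compared to care as usual" and "To compare the effectiveness between MBCT led by mindfulness teacher and that led by social workers".

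Under Data analysis, the plan has three relevant steps:

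- Baseline check: "Baseline demographic information and outcome measures among the three groups will be compared using independent sample t-test". No action is attached to the result.
- Effect analysis: "Mixed ANOVA will be used to compare outcome changes from T0 to T2 among the groups", followed by "Post-hoc analyses, such as pairwise comparisons, will be performed to identify groups with significant changes". Neither step names a covariate.
- Mechanism analysis: "If the findings demonstrate intervention effects, a regression model will be conducted to examine whether psychological flexibility" is linked to later depressive symptoms, "while controlling for baseline depression". This is the only adjustment in the plan. It is conditional on an effect being found, and it does not estimate an arm effect.

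The Outcomes section says that demographics are recorded at baseline but does not list the items.

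**The concern.** Without randomisation, nothing makes the arms alike at baseline even on average, so the analysis has to deal with differences in who entered each arm. The mixed ANOVA does part of this. Because T0 is one of its time levels, any baseline difference that would have persisted unchanged cancels out of the comparison of change.

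Two kinds of difference do not cancel. One is a baseline gap that would have shrunk anyway through regression to the mean, which is plausible when entry requires a PHQ-9 score of 5 or more. The other is an arm difference in a measured factor, such as age or centre type, that predicts how much people change. Both would be read as an effect of MBCT, or of who led it.

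The baseline check does not fill this gap. An independent-samples t-test compares two means, there are three groups, and the test would not suit a categorical demographic. Since no response to imbalance is stated, any response would be chosen after the data had been seen.

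**Working it through.** **Inputs.** From the documents: 32 per arm, three arms (3 × 32 = 96, which agrees with the stated total), and assessments at T0, T1 and T2. The documents give no significance level, SD, correlation, baseline gap or covariate strength. Everything else below is therefore assumed: two-sided 5% tests, unit SD, no true effect, correlation r = 0.5 (range 0.4 to 0.7), and gaps g of 0.3 and 0.5 SD. Results are from simulation (40,000 runs for two arms, 20,000 for three) unless stated.

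**1. A baseline gap in the outcome, two arms.** Let the gap at follow-up be s × g, with s = 1 (stable), (1 + r)/2 (midway) or r (full regression). The bias in change is (s − 1) × g. The standard error is √[2(1 − r) × 2/32], which is 0.25 at r = 0.5.

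Hand check, full regression: the bias is −0.15 or −0.25 SD, so the bias is 0.6 or 1.0 standard errors. The normal approximation gives rejection rates of 9.2% and 17.0%; simulation gives 9.0% and 16.7%.

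| Rejection rate at r = 0.5, g = 0.3 / 0.5 | Stable | Midway | Full regression |
|---|---|---|---|
| Change comparison, two arms | about 5% / 5% | 5.9% / 7.6% | 9.0% / 16.7% |
| Three-arm, three-time group-by-time F test | 5.0% / 5.0% | 5.8% / 7.1% | 8.4% / 15.2% |
| Baseline-adjusted model, two arms | 10.4% / 19.5% | 6.2% / 8.6% | 5.0% / 5.1% |

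In the F-test row, usual care differs from both MBCT arms. Over r = 0.4 to 0.7, full regression gives 7.4% to 10.0% for g = 0.3 and 11.6% to 18.8% for g = 0.5 in the change comparison. The two models fail in opposite situations, and the documents cannot say which one applies.

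**2. No gap in the outcome, but a covariate that differs between arms and predicts change.** The bias is slope × covariate gap, with a within-arm SD of change of 1. For slope 0.3 and gap 0.5 it is 0.15 SD, or 0.6 standard errors.

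| Slope (SD of change per SD) | 0.1 | 0.2 | 0.3 | 0.4 |
|---|---|---|---|---|
| Covariate gap 0.3 SD | 5.2% | 5.5% | 6.4% | 7.5% |
| Covariate gap 0.5 SD | 5.5% | 6.7% | 9.0% | 12.5% |

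Adding a covariate-by-time term brings every cell back to 4.8% to 5.1%. A covariate main effect alone would not help: a variable that is constant within a person shifts all of that person's scores equally, so in complete data the group-by-time estimates do not move.

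**3. What the baseline check would find.** For one pair of arms the noncentrality is g × √(32/2) = 4g, that is 1.2 or 2.0. Power is 21.9% or 50.4%. If usual care differs from both MBCT arms, at least one of three pairwise t-tests flags the gap in 35.5% or 67.9% of trials. With no gap at all, at least one flags in 12.2%, for each variable tested.

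**4. What agreement between models would show.** With an unmeasured shift in change of 0.15 or 0.25 SD and no baseline gap, the change model and the baseline-adjusted model both reject in 6.1% or 12.5% of trials, against 2.6% with no shift. Agreement is therefore no protection against unmeasured selection.

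**The case against.** The strongest defence is that the main model is sound. A repeated-measures comparison that includes T0 is a recognised choice for non-randomised arms, and it removes stable differences whether measured or not. The largest rates above come from the full-regression case, and in the stable case adjustment for baseline does worse than the planned analysis. This stands: the figures give no reason to replace the mixed ANOVA.

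It can also be said that covariate adjustment corrects little. Six of the eight covariate cases reject at 7.5% or less, and nothing in the documents makes the stronger slopes likely. This stands as well, and it is why the bias is described as unknown. It does not justify leaving measured predictors of change unused when they are already being collected.

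The t-test wording can be read as three pairwise tests, which is workable for continuous items and touches no effect estimate. That makes it a minor point. The low chance of detecting a relevant gap and the absence of any stated consequence remain.

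Finally, the plan is open about its design, and no analysis can remove unmeasured selection. That is correct, but it limits what adjustment can achieve; it is not a reason to omit adjustment for what is measured.

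**Conclusion.** The concern holds and should be fixed. As written, measured differences between arms that predict change stay in the estimates for both between-arm objectives, and the only safeguard is a weak check with no consequence.

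The omission is certain from the text. Its effect is not: the size and direction of any bias depend on gaps, correlations and slopes that the documents do not give. Over the assumed range, the false-positive rate runs from no inflation to about 19% for a baseline gap and about 13% for a covariate gap, and several cases show little or none. The t-test wording alone would be minor.

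**What to change.** 1. Prespecify a short list of baseline covariates already collected, not chosen by significance: age, sex and other prognostic demographics if recorded. Include centre type (DECC or ICCMW) only if it does not coincide with arm. The Intervention section describes usual care in both centre types but does not give the mix for the MBCT arms. Enter each covariate with a covariate-by-time term so that it acts on change.
2. Keep the mixed ANOVA as the main analysis and report a baseline-adjusted analysis of T1 and T2 as a sensitivity analysis. State that the first assumes baseline gaps are stable and the second that they regress, and interpret any disagreement in that light. Do not require both to be significant, and do not call agreement robust.
3. Replace the t-tests with a three-group baseline table showing standardised differences. If tests are wanted, use one-way ANOVA for continuous items and chi-square for categorical ones.
4. Word conclusions as adjusted associations from a non-randomised comparison.

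**Cost.** Revised text, one extra analysis to report, and a few degrees of freedom out of 96; no new data. For a true 0.5 SD difference in change (r = 0.5), power is 51% without covariates (93 error degrees of freedom). With four covariates that predict nothing (89) it is about 49% to 50%, and about 47% to 48% if one of them differs by 0.5 SD between usual care and both MBCT arms. These figures assume complete data and one degree of freedom per covariate; multi-category items or missing values would cost more. The team must confirm which demographics are recorded and how centre type relates to arm.
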